11 TOXICITIES/SIDE EFFECTS

The most frequently reported side effect for the study drug metformin is gastrointestinal toxicity, more specifically flatulence and/or diarrhea. These side effects generally subside within several weeks of initiation of treatment and the risk of these side effects can be decreased through a dose-escalation phase such as the one built into the proposed trial. Gastrointestinal toxicity will be measured for all patients following initiation of metformin

treatment, and will be used as the primary measure for the Phase I component of the proposed trial.

Due to its mechanism of action (see above), the risk of hypoglycemia with metformin treatment is very low. However, since patients in this trial may experience a low caloric intake due to the side effects of the conventional treatment component (cisplatin- nausea, mucositis; radiation- xerostomia, altered taste) patients will undergo weekly blood glucose monitoring. If based on these lab values or associated symptoms, the treating physician diagnoses hypoglycemia, study drug treatment will be halted, while concurrent chemoradiation will continue. Once blood glucose normalizes, metformin will be restarted and the dose should be decreased by 250mg with daily monitoring of blood glucose. If there are no symptoms or signs of hypoglycemia in 1 week, daily monitoring will be discontinued. All dose de-escalation and re-escalation will be recorded in source documentation. Hypoglycemia will be measured for all patients following initiation of metformin treatment, and will be used as a secondary measure for the Phase I component of the proposed trial.

Toxicity recording will commence once patients start taking metformin and will be completed at 30days following completion of treatment.

12.0 MEASUREMENT OF EFFECT

Response and progression will be evaluated using the new international criteria proposed by the Response Evaluation Criteria in Solid Tumors (RECIST1.1) Committee [Eur J Cancer. 2009 Jan; 45(2):228-47]. Changes in only the largest diameter (uni-dimensional measurement) of the tumor lesions are used in the RECIST 1.1 criteria.

12.1 Antitumor Effect – Solid Tumors

For the purposes of this study, patients should be reevaluated for response following completion of treatment as per current institutional protocol for this disease site: 1) spiral contrast enhanced computed tomography (CECT) at 8-10 weeks following completion of treatment or 2) positron emission tomography (PET) at 10-12 weeks following completion of treatment. No additional imaging or tests will be performed as part of the current protocol. Following the first post treatment scan, patients will continue routine surveillance using CECT or PET per institutional protocols.

12.1.1. Definitions

Evaluable for toxicity. All patients will be evaluable for toxicity from the time of their first treatment with metformin until 30 days following treatment completion.

Evaluable for objective response. All patients included in the study must be assessed for response to treatment, even if there are major protocol

treatment deviations. These patients will have their response classified according to the definitions stated below.

12.1.2 Disease Parameters

Measurable disease. Measurable lesions are defined as those that can be accurately measured in at least one dimension (longest diameter to be recorded) as ≥ 10 mm with spiral CECT scan. All tumor measurements must be recorded in millimeters (or decimal fractions of centimeters).

Non-measurable disease. All other lesions (or sites of disease), including small lesions (longest diameter < 10 mm using spiral CECT scan), are considered non-measurable disease. Bone lesions, leptomeningeal disease, ascites, pleural/pericardial effusions, lymphangitis cutis/pulmonis, inflammatory breast disease, abdominal masses (not followed by CT or MRI), and cystic lesions are all non-measurable.

Target lesions. All measurable lesions up to a maximum of 5 lesions per organ and 10 lesions in total, representative of all involved organs, should be identified as target lesions and recorded and measured at baseline. Target lesions should be selected on the basis of their size (lesions with the longest diameter) and their suitability for accurate repeated measurements (either by imaging techniques or clinically). A sum of the longest diameter (LD) for all target lesions will be calculated and reported as the baseline sum LD. The baseline sum LD will be used as reference by which to characterize the objective tumor response.

Non-target lesions. All other lesions (or sites of disease) including any measurable lesions over and above the 10 target lesions should be identified as non-target lesions and should also be recorded at baseline. Measurements of these lesions are not required, but the presence or absence of each should be noted throughout follow-up.

12.1.3 Methods for Evaluation of Measurable Disease

All measurements should be taken and recorded in metric notation using a ruler or calipers. All baseline evaluations should be performed as closely as possible to the beginning of treatment and never more than 4 weeks before the beginning of the treatment. The same method of assessment and the same technique should be used to characterize each identified and reported lesion at baseline and during follow-up. Imaging-based evaluation is preferred to evaluation by clinical examination when both methods have been used to assess the antitumor effect of a treatment.

Spiral contrast enhanced CT. Spiral CT should be performed using the approved institutional head and neck protocol.

Ultrasound (US). When the primary endpoint of the study is objective response evaluation, US should not be used to measure tumor lesions. It is, however, a possible alternative to clinical measurements of superficial palpable lymph nodes, subcutaneous lesions, and thyroid nodules. US might also be useful to confirm the complete disappearance of superficial

lesions usually assessed by clinical examination.

Endoscopy. The utilization of this technique for objective tumor evaluation has not yet been fully and widely validated. Its use in this specific context require sophisticated equipment and a high level of expertise that may only be available in some centers. Therefore, the utilization of such a technique for objective tumor response should be restricted to validation purposes. However, such a technique may be useful to confirm complete pathological response when biopsies are obtained.

Tumor markers. Tumor markers alone cannot be used to assess response.

Cytology, Histology. These techniques can be used to differentiate between partial responses (PR) and complete responses (CR) in rare cases (e.g., residual lesions in tumor types, such as germ cell tumors, where known residual benign tumors can remain). The cytological confirmation of the neoplastic origin of any effusion that appears or worsens during treatment when the measurable tumor has met criteria for response or stable disease is mandatory to differentiate between response or stable disease (an effusion may be a side effect of the treatment) and progressive disease.

12.1.4 Response Criteria

12.1.4.1 Evaluation of Target Lesions

Complete Response (CR): Disappearance of all target lesions

Partial Response (PR): At least a 30% decrease in the sum of the longest diameter (LD) of target lesions, taking as reference the baseline sum LD

Progressive Disease (PD): At least a 20% increase in the sum of the LD of target lesions, taking as reference the smallest sum LD recorded since the treatment started or the appearance of one or more new lesions

Stable Disease (SD): Neither sufficient shrinkage to qualify for PR nor sufficient increase to qualify for PD, taking as reference the smallest sum LD since the treatment started

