12.1.5 Duration of Response

Duration of overall response: The duration of overall response is measured from the time measurement criteria are met for CR or PR (whichever is first recorded) until the first date that recurrent or progressive disease is objectively documented (taking as reference for progressive disease the smallest measurements recorded since the treatment started). The duration of overall CR is measured from the time measurement criteria are first met for CR until the first date that recurrent disease is objectively documented. Duration of stable disease: Stable disease is measured from the start of the treatment until the criteria for progression are met, taking as reference the smallest measurements recorded since the treatment started.

12.1.6 Progression-Free Survival: Defined as the duration of time from the date of study registration to the date of documented radiographic progression.

12.1.7 Overall survival: Defined as the duration of time from the date of study registration to the date of the patient’s death due to any cause.

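### Target-lesion PD is a 20% rise over the smallest sum with no millimetre minimum, so for small residuals after chemoradiation the PD trigger lies within plausible reading error

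*Combined protocol and SAP*

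**What the plan says.** Section 12.1.4.1 calls target-lesion PD when there is "At least a 20% increase in the sum of the LD of target lesions". The comparison is with the running minimum, worded as "taking as reference the smallest sum LD recorded since the treatment started". The appearance of new lesions is the alternative route to PD. No absolute minimum increase appears there or elsewhere in the document.

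Two passages compete over which rule applies. Section 12.0 states "Response and progression will be evaluated using the new international criteria proposed by the Response Evaluation Criteria in Solid Tumors (RECIST1.1) Committee", but does not reproduce that source's PD rule. Section 12.1.1 states "These patients will have their response classified according to the definitions stated below", which points to the rule as written.

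A lesion is measurable at baseline if its longest diameter is recorded "as ≥ 10 mm with spiral CECT scan" (12.1.2). The same section says "All tumor measurements must be recorded in millimeters (or decimal fractions of centimeters").

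Section 12.1.6 runs PFS from registration "to the date of documented radiographic progression" and requires no confirmation. Section 12.1.5 uses the smallest recorded measurements as the reference for duration of response too. Section 12.1.4.2 provides for later confirmation of progression, but only for non-target lesions.

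**The concern.** A purely relative threshold shrinks with the lesion. Target lesions can enter at 10 mm and are then irradiated to about 70 Gy, so some patients without a complete response may be followed with a small residual sum. For them, 20% of the sum is one to three millimetres.

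The reference is a running minimum, so a single low reading lowers the bar for every later scan. Readings of 10, 10 and 12 mm are PD (12/10 = 1.20), and so are 8, 7 and 9 mm (9/7 = 1.286). Neither sequence need mean growth.

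What is at stake is PFS, a listed secondary endpoint whose only event is radiographic progression, and duration of response. A false PD call ends both early.

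**Working it through.** The plan states no error rate for its PD rule, so there is no figure to reproduce.

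**Inputs from the document.** Threshold 20% over the smallest sum (12.1.4.1); 10 mm minimum lesion size at baseline (12.1.2); no confirming scan (12.1.6).

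**Assumptions.** A truly constant sum S; independent normal reading error on the sum with SD s, taken over 0.5-2 mm; three or five post-treatment scans. The document gives none of these.

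**Trigger size.** Required rise = 0.20 x smallest sum:

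| Smallest sum (mm) | 5 | 8 | 10 | 15 | 20 | 25 | 40 |
|---|---|---|---|---|---|---|---|
| Rise called PD (mm) | 1.0 | 1.6 | 2.0 | 3.0 | 4.0 | 5.0 | 8.0 |

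A single 10 mm target lesion that just reaches PR measures 10 x 0.70 = 7 mm, and is PD again at 7 x 1.2 = 8.4 mm. A 40 mm lesion that just reaches PR measures 28 mm and needs a 5.6 mm rise.

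**One comparison.** With errors e1 and e2, PD is called if S + e2 >= 1.2(S + e1), that is, e2 - 1.2 e1 >= 0.2 S. The left side has SD s x sqrt(1 + 1.44) = 1.562 s, so P(false PD) = 1 - Phi(0.2 S / 1.562 s).

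- S = 10, s = 1: 2/1.562 = 1.280, giving 10%.
- S = 10, s = 0.5: 2/0.781 = 2.561, giving 0.5%.
- S = 5, s = 1: 1/1.562 = 0.640, giving 26%.
- S = 25, s = 1: 5/1.562 = 3.201, giving under 0.1%.

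**Several scans against the running minimum.** Simulation, 400,000 patients per cell, five post-treatment scans (the first sets the reference, four follow), unrounded readings:

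| True sum | SD 0.5 mm | SD 1 mm | SD 1.5 mm | SD 2 mm |
|---|---|---|---|---|
| 10 mm | 4% | 50% | 74% | 85% |
| 15 mm | 0.1% | 18% | 50% | 69% |
| 20 mm | <0.1% | 4% | 27% | 50% |
| 25 mm | <0.1% | 0.6% | 12% | 32% |
| 10 mm, with 5 mm minimum | <0.1% | 0.2% | 7% | 25% |

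**Rounding.** Section 12.1.2 permits whole millimetres or decimals of a centimetre. Whole-millimetre rounding raises the rates because 10 to 12 mm lands exactly on 20%. For a 10 mm sum, unrounded to rounded:

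- SD 1 mm: about 23-33% over three scans and 50-63% over five.
- SD 0.5 mm: about 1.5-7% and 4-19%.

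With a 5 mm minimum, rounded readings at SD 1 mm give 0.3% over three scans and 0.8% over five.

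**Where a minimum acts.** A minimum of m mm is the stricter condition only when 0.20 x smallest sum < m, so below 5m: below 25 mm for m = 5, below 15 mm for m = 3.

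**The case against.** **The citation may already cover it.** Section 12.0 names RECIST 1.1, and whether that source sets an absolute minimum cannot be settled from the document. This stands as a reason to reconcile the texts. It does not remove the problem, because 12.1.1 directs the reader to the written definitions, and those hold only the 20% rule.

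**Small residuals may be uncommon.** Enrolment is stage III/IV, Appendix A includes primaries over 4 cm and nodes up to and beyond 6 cm, up to ten target lesions are summed, and patients in complete response have no residual sum. This stands: a reader might infer that residual sums are often small, but the document says nothing about their size.

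**The number of scans is uncertain.** The study calendar marks imaging at the post-study visits and 12.1 refers to routine surveillance. Section 9.3.1 recommends imaging at those visits if progression is suspected. A reader might treat three to five scans as a cautious count from the calendar alone; the conflict with 9.3.1 does not allow that.

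**Other safeguards.** Same-technique measurement (12.1.3) and blinded radiology review (12.1.7) may reduce reading error, but neither changes the threshold. Biopsy is recommended in 9.3.3 but forms no part of the PD or PFS definition.

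**Little depends on it.** Section 13.4 calls the secondary analyses exploratory, and Section 13 names disease-free survival rather than PFS. This limits the importance of the point.

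**Conclusion.** The point holds for patients with a small residual short of complete response. For sums of about 5-15 mm, the written rule can turn a 1-3 mm reading difference into a progression date. The rates rest on the assumed SD, independence between scans, the number of scans and rounding. They range from a few per cent at SD 0.5 mm to half or more over five scans at SD 1 mm for a 10 mm sum. At a 25 mm sum and SD 1 mm they are under 1%.

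A reader might go further and infer that PFS in this trial will be materially biased downward. The document does not support that: without the distribution of residual sums and the actual number of scans, the number of false events cannot be derived. The direction is toward shorter PFS and shorter duration of response; the size is unknown.

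Nor does the problem reach the primary endpoint. PR is judged against baseline, no earlier post-treatment scan is planned to set a lower reference, and SD and PD both count as non-response (13.2).

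**What to change.** In 12.1.4.1, require for target-lesion PD both the 20% relative rise over the smallest sum and an absolute increase in the sum LD of at least a stated minimum. Five millimetres is proposed here as an assumption, not a figure from the document; it matters only when the smallest sum is below 25 mm. Leave PD by new lesions and by unequivocal non-target progression unchanged. State whether 12.1.4.1 or the criteria cited in 12.0 govern, and make the two agree.

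The cost is one clause and one reconciling sentence. True growth of a very small residual may be called PD one visit later. The minimum does not remove all false calls: at SD 2 mm, a stable 10 mm sum would still be called PD in about 25% of patients over five scans.

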12.1.4.2 Evaluation of Non-Target Lesions

Complete Response (CR): Disappearance of all non-target lesions and normalization of tumor marker level Note: If tumor markers are initially above the upper normal limit, they must normalize for a patient to be considered in complete clinical response.

Incomplete Response/Stable Disease (SD): Persistence of one or more non-target lesion(s) and/or maintenance of tumor marker level above the normal limits

Progressive Disease (PD): Appearance of one or more new lesions and/or unequivocal progression of existing non-target lesions.

Although a clear progression of “non-target” lesions only is exceptional, the opinion of the treating physician should prevail in such circumstances, and the progression status should be confirmed at a later time by the review panel (or Principal Investigator).

12.1.4.3 Overall Response: overall response will be ascertained via clinical exam and imaging at 8-12 weeks post treatment completion according to the table below.

Target Lesions	Non-Target Lesions	New Lesions	Overall Response (measured at 8-12wk post treatment)
CR	CR	No	CR
CR	Non-CR/Non-PD	No	PR
PR	Non-PD	No	PR
SD	Non-PD	No	SD
PD	Any	Yes or No	PD
Any	PD*	Yes or No	PD
Any	Any	Yes	PD

* In exceptional circumstances, unequivocal progression in non-target lesions may be accepted as disease progression.

Note: Patients with a global deterioration of health status requiring discontinuation of treatment without objective evidence of disease progression at that time should be reported as “*symptomatic deterioration*”. Every effort should be made to document the objective progression even after discontinuation of treatment.

12.1.5 Duration of Response

Duration of overall response: The duration of overall response is measured from the time measurement criteria are met for CR or PR (whichever is first recorded) until the first date that recurrent or progressive disease is objectively documented (taking as reference for progressive disease the smallest measurements recorded since the treatment started). The duration of overall CR is measured from the time measurement criteria are first met for CR until the first date that recurrent disease is objectively documented. Duration of stable disease: Stable disease is measured from the start of the treatment until the criteria for progression are met, taking as reference the smallest measurements recorded since the treatment started.

12.1.6 Progression-Free Survival: Defined as the duration of time from the date of study registration to the date of documented radiographic progression.

12.1.7 Overall survival: Defined as the duration of time from the date of study registration to the date of the patient’s death due to any cause.

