2.2 Secondary Objectives

Secondary endpoints for the phase II component will include: progression free survival and overall survival.

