9.3 Evaluation following treatment

9.3.1 A brief history and physical examination by a medical, radiation or surgical (ENT or Head and Neck Surgery) oncologist, including laryngopharyngoscopy (mirror and/or fiberoptic and/or direct procedure), should be done at 10 weeks following completion of radiation then every 3 months through year 1 and every 4 months through year 2. A 30 day visit or telephone interview is required for evaluation of Adverse Events. Radiographic imaging (CT, MRI, or PET as appropriate) at these time points is highly recommended if disease progression is suspected by the treating physician. If performed, radiographic imaging to evaluate the patient for both local-regional recurrence and distant metastases is highly recommended.

- 9.3.2 Chest imaging: A chest CT or a PET/CT of chest is recommended once per year.
- 9.3.3 Biopsy of any lesion(s) suspicious for tumor recurrence is recommended as clinically indicated.
- 9.3.4 The initial post-radiation imaging evaluation (CT at 8-10weeks or PET-CT at 10-12weeks) after the completion of chemoradiation is recommended to assess disease response. The imaging can be contrast enhanced CT (neck and chest) or PET-CT of the head and neck or “whole body” PET/CT (minimum neck and chest) based on the preference of the treating clinician, but must be consistent with the pre-treatment imaging modality.

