9.2 Study Calendar

	Pre-study	wk -2 (d3+/-2d)	wk 1 (d3+/-2d)	wk 2 (d3+/-2d)	wk 3 (d3+/-2d)	wk 4 (d3+/-2d)	wk 5 (d3+/-2d)	wk 6 (d3+/-2d)	wk 7 (d3+/-2d)	30 days post radiation completion	Post-study (wk17+/-2wk)	Post-study (yr1 Q3mos)	Post-study (yr2 Q4mos)
Metformin tx		<-----BID metformin----->											
Chemo-radiation tx			<-----XRT (Daily); chemotherapy (weekly)----->										
Collected information (ONCORE)													
Metformin pill diary/compliance form		x	x	x	x	x	x	x	x				
Eligibility checklist	x												
Informed consent	x												
T, N, M staging	x												
Demographics	x												
Physical Exam	x	x	x	x	x	x	x	x	x		x	x	x
Medical history	x												
Vital signs	x										x	x	x
Weight	x	x	x	x	x	x	x	x	x		x	x	x
Performance status	x	x	x	x	x	x	x	x	x		x	x	x
Adverse event evaluation		x	x	x	x	x	x	x	x	x	x		
CMP	x												
CBC, BMP	x	x	x	x	x	x	x	x	x		x	x	x
Glucose monitoring (if applicable) (A)		x	x	x	x	x	x	x	x				
Disease response/radiologic evaluation											x	x	x
Pregnancy test	x (B)												
Imaging (C)	x										x	x	x
Laryngopharyngoscopy											x	x	x
pre-study items to be collected within 30 days of initiation of metformin treatment													
Pill diary/compliant may be discussed or completed via telephone.													
A: patients with hypoglycemia (<=60mg/dl) will receive instructions and supplies for BID glucose monitoring and recording													
B: Serum or urine pregnancy test (women of childbearing potential).													
C: Required within 8-12 weeks prior to registration, at end of radiation treatment, and at regular intervals following treatment completion.													
D= day, Wk= week, Mos= months, Yr= year; d3+/-2d= to be completed on day 3 of any given week, +/- 2days													

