13.0 STATISTICAL CONSIDERATIONS

13.1 Study Design/Endpoints

This is a single arm combination Phase I/II trial of Metformin to determine the maximum tolerated dose (MTD) of metformin among 2 dose levels (850mg, 1500mg administered orally, twice daily) and to evaluate the disease response rate at the MTD. Standard of care conventional chemotherapy (cisplatin) will be administered using current clinical protocols. Dose-limiting toxicity will be ascertained using the Common Terminology Criteria for Adverse Events v4.0. The dose-limiting toxicities ascertained for the phase I component will be gastrointestinal toxicity and hypoglycemia requiring dose reduction. The primary outcome for the phase II component will be disease response rate (RECIST criteria) at 8-12 weeks post treatment completion.

The secondary outcomes will be disease free and overall survival. All analysis of secondary studies will be performed post hoc and will not be used to influence clinical decision making during the therapeutic trial.

This study began as a Phase I “3+3”/ Phase II “Simon” design, but was converted into Bayesian Optimal Interval (BOIN) design before completion of the Phase I to provide monitoring of toxicity beyond the Phase I cohort. BOIN design has algorithmic escalation/de-escalation rules easy to implement like a traditional 3+3 design but allows for specification of the target DLT rate, different size cohorts, is more likely to correctly select the MTD and allocate more patients to the MTD and expands consistent toxicity monitoring to the entire cohort. BOIN design with a target DLT rate of 0.3 and cohort size of 3 begins exactly in the same fashion as the “3+3” allowing for the implemented design change in early stages. Calculations were done using R package BOIN.³²

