13.4 Analysis of Secondary Endpoints

Secondary endpoints including disease free and overall survival will be analyzed by Kaplan-Meier method. All of the analyses will be considered exploratory in nature.

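### PFS as defined in Section 12.1.6 leaves out death, so it is time to radiographic progression and can read too high; Sections 13.1 and 13.4 name an undefined disease-free survival instead

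*Combined protocol and SAP*

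**What the plan says.** Section 2.2 sets the secondary objectives: "Secondary endpoints for the phase II component will include: progression free survival and overall survival". Section 1.0 agrees.

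Section 12.1.6 then defines PFS: "Defined as the duration of time from the date of study registration to the date of documented radiographic progression". The definition of overall survival (OS) directly below it ends at death from any cause. No censoring rule is given for PFS.

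The statistical section uses another name. Section 13.1 states: "The secondary outcomes will be disease free and overall survival". Section 13.4 states: "Secondary endpoints including disease free and overall survival will be analyzed by Kaplan-Meier method". It adds: "All of the analyses will be considered exploratory in nature". Disease-free survival has no definition anywhere in the document.

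On follow-up, Section 9.3.1 says that imaging at the follow-up visits "is highly recommended if disease progression is suspected by the treating physician". Section 9.3.3 says: "Biopsy of any lesion(s) suspicious for tumor recurrence is recommended as clinically indicated". Footnote C of the Study Calendar requires imaging before registration, "at end of radiation treatment, and at regular intervals following treatment completion".

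**The concern.** PFS is meant to describe how long patients stay both alive and free of progression. With radiographic progression as the only event, a patient who dies before any scan shows progression never contributes an event. In a Kaplan-Meier analysis such a patient would be censored, as if still at risk of a later progression. The curve would then sit above true PFS, and a reader comparing it with PFS from elsewhere would be misled.

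The same wording leaves out recurrence shown only by biopsy or examination. It becomes an event when a scan later confirms it, or never if no scan follows.

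The naming conflict makes this worse. An analyst who follows Section 13 must decide when disease-free survival starts, who is in the population and what the events are. Every patient enters with measurable disease (Section 4.0, item b), so the start could be registration or the date of complete response. Section 13.1 says the secondary analyses are done post hoc, so this choice could be made with the data in hand.

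**Working it through.** **1. Is death counted anywhere else as a PFS event?** The nearest text is Section 13.5.2, which treats early deaths (categories 5 to 7) as treatment failures. It does so for the response rate only and does not amend Section 12.1.6. Section 12.1.5 ends duration of response at objectively documented recurrence or progression, which is wider than the radiographic event in Section 12.1.6. A biopsy-proven recurrence could therefore end a response without being a PFS event.

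**2. There is no planned figure to reproduce.** The documents give no PFS rate, event count or power for this endpoint. What follows is illustration under stated assumptions.

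**3. Bounds from counts.** Inputs: n = 28 (Section 13.2, patients at the maximum tolerated dose). Assumed: 14 first events by two years, no other censoring before then, and k of the 14 are deaths without a progression scan, so 14 − k are progressions.

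- True PFS, with death as an event: (28 − 14)/28 = 50%, whatever k is.
- Deaths censored, all before the progressions: the risk set is 28 − k and 14 patients remain event-free, giving 14/(28 − k). This is the minimum.
- Deaths censored, all after the progressions: (28 − (14 − k))/28 = (14 + k)/28. This is the maximum.

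| k | Minimum | Maximum | True PFS |
|---|---|---|---|
| 0 | 14/28 = 50.0% | 14/28 = 50.0% | 50% |
| 1 | 14/27 = 51.9% | 15/28 = 53.6% | 50% |
| 2 | 14/26 = 53.8% | 16/28 = 57.1% | 50% |
| 4 | 14/24 = 58.3% | 18/28 = 64.3% | 50% |

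**4. Proportional cause-specific hazards.** If a fraction f of first events are such deaths, the curve with deaths censored tends to S^(1 − f), where S is true PFS. With S = 0.5 and f = 10%, 20%, 30%, 40%: 0.5^0.9 = 53.6%, 0.5^0.8 = 57.4%, 0.5^0.7 = 61.6%, 0.5^0.6 = 66.0%.

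**5. A second set of assumptions.** Take n = 28 with 8 progressions at months 4, 5, 6, 8, 10, 12, 15 and 19, and everyone else followed to month 24.

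- One death at month 9: censored, (24/28) × (19/23) = 70.8%; counted, 19/28 = 67.9%.
- Four deaths at months 3, 7, 11 and 17: censored, 68.8%; counted, 16/28 = 57.1%.

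With constant hazards, two-year progression of 20–40% and death without progression of 5–20%, the curve with deaths censored is 3.8 to 17.5 points too high.

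**6. Does the direction depend on the unwritten censoring rule?** In the one-death example, dropping the patient gives 19/27 = 70.4%, and counting the patient as never progressing gives 20/28 = 71.4%. Both exceed 67.9%.

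**7. Sampling error for scale.** At 50% with n = 28, the standard error is √(0.5 × 0.5/28) = 0.094, or about 9.4 points.

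**The case against.** The strongest reply is that little depends on this endpoint. It is secondary and exploratory, in a single-arm trial with no planned PFS comparison, threshold or power, and OS counts every death. The shift from one or two deaths in the illustration, about 2 to 7 points, is within one standard error. All of that stands and limits the weight of the point. It does not remove it: the error goes in one direction, and a confidence interval reflects random error without showing bias.

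A second reply is that disease-free survival is probably a slip for the PFS of Section 12.1.6. That is plausible, but it is not written, and it leads back to a definition without death.

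A third is that the Study Calendar marks imaging at week 17, every 3 months in year 1 and every 4 months in year 2, so progression would seldom be missed. The grid does give visits. The conditional wording of Section 9.3.1 conflicts with it, and Section 12.1 refers to routine surveillance under institutional protocols. Even regular scans would not capture a death between visits.

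Finally, the event numbers are assumed. The highest figures need 4 of 14 (about 29%) or 40% of first events to be deaths without a progression scan, and nothing in the documents supports a particular rate. That is correct, and the figures should be read only as a scale.

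**Conclusion.** The concern holds. As written, Section 12.1.6 defines time to radiographic progression, and Section 13 plans to analyse an endpoint that is not defined. Leaving aside recurrences shown only by biopsy or examination, the curve equals true PFS if no patient dies without a progression scan and lies above it after any such death. This direction does not rest on the assumed rates, and in the worked example it did not depend on how the death was handled. The size does rest on them: with 28 patients and true PFS of 50%, about 2 to 4 points for one such death and 8 to 14 points for four. The text should be corrected before the secondary analysis is run. The response decision rule, the sample size and OS are unaffected.

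**What to change.** - In Section 12.1.6, define PFS as the time from registration to the first of documented progression or recurrence (by imaging or biopsy) or death from any cause. Censor patients without an event at their last disease assessment.
- In Sections 13.1 and 13.4, replace disease-free survival with PFS, to match Sections 1.0 and 2.2. If the sponsor does want disease-free survival as well, give it its own start date, population and events.
- If time to progression is also reported, label it as such and treat death as a competing event.
- Reconcile Section 9.3.1 with footnote C of the Study Calendar, and with Section 12.1, so that the assessment schedule behind PFS is stated once.

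The cost is protocol wording. OS already needs the date of death, but the Study Calendar lists no survival-status item, so check that the case report form records it. Reported PFS may be lower than under the present text.
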